17.2. DESCRIPTIVE STATISTICS

Descriptive statistics will be calculated using as reference the number of subjects in the relevant analysis population (any exception will be specified) according to the nature of the data as follows:

- Continuous variables: number of non-missing observations, arithmetic mean, standard deviation, 95% CI, minimum and maximum values, median and quartiles (Q1, Q3).
If there are fewer than 5 observations only the number of non-missing observations, arithmetic mean, median, minimum and maximum will be presented.
- Categorical variables: Number of non-missing observations, the number of missing and the relevant percentage on the analysis population, number and relative frequencies. If not defined otherwise, the percentage denominator will be the number of subjects with non-missing information.

In case of subcategories, the relative frequencies will be calculated on the basis of the subjects in the respective category, in this case a footnote will be added explaining the different denominators.

For presentation of missing data, please see section 6.10.

17.3. PERCENTAGES AND DECIMAL PLACES

For continuous variables, minimum and maximum will be presented to the same precision as the raw data. Mean, median, Q1 and Q3 will be presented to one more decimal place and standard deviation to two more decimal places than the raw data.

For categorical variables, percentages will be presented up to two decimal places.

17.4. PRESENTATION OF DATES

Calendar dates and times (optional) in all the listings will be displayed in the format:

YYYY-MM-DD Thh:mm:ss e.g. 2011-01-15 T10:20:23.

Note: If time is not collected, calendar dates will be displayed as: YYYY-MM-DD.

17.5. TIME UNITS

The standard unit of time for this study will be days, unless otherwise specified.

In case duration is to be reported in months, duration in days is divided by 30.4375.

If duration is to be reported in years, duration in days will be divided by 365.25.

17.6. GENERAL CONVENTIONS FOR MISSING DATA

For the statistical analysis, some particular data handling conventions (handling of missing data, pooling of centers) are planned. The details are present in the respective Sections. While presenting summary statistics and in Listings the following conventions will be used with respect to missing data:

Missing data	Will be reported as "Not Available"
--------------	-------------------------------------

LEVEA – Statistical Analysis Plan

Data reported as, "Not done", "Asked but unknown", "Not asked"	Will be reported as " Unknown"
Data reported as "Not applicable", "Measurement failed"	Will be reported as "Not applicable"
Reported data is not valid	Will be reported as invalid data
Adverse events Missing or partially missing start date	Missing day NK-MMM-YYYY To be imputed by: 1st day of the month Missing day and month NK-NK-YYYY To be imputed by: 1 st Day of the year. Totally missing date NK-NK-NK To be imputed by: Reference Start date. Should not happen, should have been clarified at the data level. In case of not resolved.

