4.3. STUDY DURATION

Each subject will participate in the study for maximum 3 months.

As the study plans an inclusion period of approximately 3 months, the study duration is approximately 6 months.

The Sponsor may perform adjustments/enhancements to the study CIP or eCRF as deemed appropriate in order to guarantee consistency to the main study endpoints. Whenever relevant and required, the EC and the Competent Authorities (CA) shall be notified by the investigator about any change made to the study.

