10.2. PRINCIPAL INVESTIGATOR'S RESPONSIBILITIES IN ADVERSE EVENT REPORTING

The responsibilities of the principal investigator include the following:

- The Principal Investigator is required to report the following adverse events to the Sponsor:
- Unanticipated Serious Adverse Device Effects should be reported to the Sponsor within 24 hours of awareness of the event by notifying the Sponsor Clinical Project Manager and by entering the information in the EDC. These events require urgent investigation by the Sponsor and reporting to regulatory authorities, as applicable.
- All adverse events (serious and non-serious) during the testing procedure should be reported. However, conditions that occur due to direct physiologic effects of testing (e.g. PNS, palpitations, and discomfort) are not considered adverse events.
- Serious cardiovascular and access site adverse events from inclusion (signing date of informed consent) to termination should be reported as soon as possible but no later than 3 calendar days upon awareness. The Principal Investigator should enter all available information in the “AE section” of the EDC system. Cardiovascular events refer to those that are classified under cardiac disorders, bleeding disorders, cerebrovascular, and peripheral vascular as defined in the trial-specific AE classifications (Appendix B).
- Device deficiencies should be reported within 5 calendar days of awareness. Deficiencies of the Sponsor study device should be reported in the Device Deficiencies section in EDC. The Principal Investigator must return the device, if possible, to the Sponsor. Deficiencies of the non-Sponsor study device should be reported following the commercial reporting procedure for that device.

Timelines and Communication Methods for Reporting Adverse Events

Study Period	Event Classification	Communication Method	Communication Timeline
During initial testing procedure	All adverse events e.g. procedural complications (serious and non-serious), excluding direct physiologic effects of testing	Complete AE eCRF page with all available information.	Within 3 calendar days of first becoming aware of the event
Throughout study duration	All Serious cardiovascular and access site Adverse Events	Complete AE eCRF page with all available information.	Within 3 calendar days of first becoming aware of the event

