5.2. STUDY DAY

The Inclusion date will be considered as the reference start date.

The study day describes the day of the event or assessment date, relative to the reference start date (Inclusion date).

The reference start date is designated as Study Day 1. Study Day -1 is the day that precedes Day 1. Study Day 0 is not defined.

The study day will be calculated as:

- if the event is on or after the reference start date : The date of the event (visit date, onset date of an event, assessment date etc.) - reference start date + 1.
- if the event precedes the reference start date : The date of the event (visit date, onset date of an event, assessment date etc.) - reference start date.

The study day will be displayed in the data listings.

LEVEA – Statistical Analysis Plan

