5.3. VISITS, VISIT WINDOWS AND COMPLIANCE

The study has the following scheduled visits:

- Inclusion Visit (up to 5 days post-implant for IS1 subjects and at any time post implant for IS4 subjects)
- M0 follow-up Visit (up to 15 days after inclusion visit)
- M1 follow-up visit (up to 1 to 3 months after M0 visit)

The performed visits have an analysis window defined in the protocol. Study visit days are calculated from the day of inclusion. In addition a Targeted Study Day is defined as the mid-point of the protocol defined Visit window.

Table 1: Visit Windows

Visit	Targeted study day	Analysis window in protocol	Analysis window taken into account in the statistical analysis if scheduled visit is missing
Inclusion	1	0-5 days post-implant for IS1 subjects and at any time post-implant for IS4 subjects	Latest unscheduled visit prior to M0 follow-up visit.
M0	8	0-15 days post-Inclusion Visit	Not Applicable
M1	70	30-92 days post M0 Visit	Not Applicable

All subjects not discontinued from the study on the first day of the window of a respective scheduled visit will be considered as "Eligible".

Subjects having scheduled visits in the protocol defined windows will be considered "compliant". Subjects having scheduled visits outside the protocol visit windows will be considered "non-compliant".

Number and percentage of "eligible" subjects at each visit will be presented, percentage calculated based on the study population.

Number and percentage of subjects who are compliant at each visit will also be presented, percentages will be based on number of "eligible" subjects at the respective visit.

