11. SECONDARY SAFETY ANALYSES

11.1. ASSESSMENT OF THE DEVICE CHARACTERISTICS IN TERMS OF SAFETY AND DEVICE DEFICIENCY

- A. Serious adverse device events and device deficiencies will be collected during each subject visit. Confirmation of absence of USADE during “In-Clinic LVAT” tests will be evaluated by analyzing all SAEs and device deficiencies (DD) collected at each visit.

This secondary endpoint will be based on IP.

- B. Algorithm characteristic: Underestimated Assessments

Assessment of LV pacing threshold underestimation: comparison to manual LV threshold value will be performed by comparing manual and automatic LV threshold values at each visit. An underestimated LV threshold value of “In-Clinic LVAT” feature is defined as a value result more than 2 steps below the LV threshold measured manually (meaning -0.5V if threshold<2.5V, else -1V as measured) . Please see table 6.

LEVEA – Statistical Analysis Plan

Number and percentages of “underestimated” assessments will be presented along with the exact 95% CI (Clopper & Pearson, 1934) by M0 and M1 visit. Only subjects with non-missing manual data will be considered.

The reasons for LV pacing threshold underestimation at M0 visit will be presented as table and listing. The missing reasons (if any) for underestimation will be presented as “Not available”. For the table, the number and percentages of the reasons will be presented with the denominator of the percentages based on the total number of LV pacing threshold underestimated.

Total number of attempted, completed,, Underestimated LV vector tests will be presented by LV vector for each LV pacing configuration by visit.

For the LV tests performed for patients with either IS1 and IS4 leads (six LV vectors common to IS1 and IS4) , the percentage for the number of LV vector tests “attempted”, will be calculated based on the number of patients implanted with either IS1 and IS4 leads.

For the LV tests performed for patients with IS4 leads (eight LV vectors pertaining only to IS4), the percentage for the number of LV vector tests “attempted”, will be calculated based on the number of patients implanted with IS4 lead.

For number of LV vector tests “completed”, the percentage will be calculated based on the number of LV vector tests attempted.

For number of LV vector tests “Underestimated”, the percentage calculated based on number of Complete LV vector tests .

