14.1. GENERAL RULES FOR AE REPORTING

Adverse events that occurred after the inclusion visit and prior to study termination or Lost-to follow-up will be presented for all subjects in the Safety Population.

If there are less than 10 Adverse events reported in the study, the Adverse Events will be reported only by listing.

The following Safety Events will be reported in the study based on their time of occurrence:

During initial testing procedure

- All adverse events e.g. procedural complications (serious and non-serious), excluding direct and clinically expected physiologic effects of testing

Throughout the study

- All Serious cardiovascular and access site Adverse Events
- All deaths

LEVEA – Statistical Analysis Plan

- Unanticipated (Serious) Adverse Device Effect
- Device Deficiencies (including but not limited to failures, malfunctions, and product nonconformities) with or without associated adverse events

The classification of AEs for statistical analysis will be based on site-reported events for the final diagnosis in the Safety populations.

A positive relationship (YES) will include those assessed as related or unknown if related to the device/procedure. A negative relationship (NO) will be limited to those assessed as not being related to the device/procedure.

The adverse events (AEs) in the Safety population will be assessed using descriptive statistics by

- Diagnosis (AE Category, AE Term, AE clarifiers)
- Relationship – (Yes/No)
- Device Interrogation (Yes/No)
- Treatment and Medication
- Outcome (Resolved/Death/Pending)
- Relationship: to procedure, to device
- Expectedness for ADE (Yes/No)

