- Resulted in AE (obtained from Device deficiency page of eCRF)
- Resulted in SAE

All AEs, ADEs, Device Deficiencies, SAEs and Deaths will be listed.

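### Partial adverse event start dates are imputed with no floor at inclusion, so an on-study event can be dated before inclusion and drop out of the summary tables

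*SAP*

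**What the plan says.** SAP 17.6 gives three rules for adverse event start dates:

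- Day unknown: "Missing day NK-MMM-YYYY To be imputed by: 1st day of the month".
- Day and month unknown: the first day of the year.
- Date totally missing: the reference start date. SAP 5.2 defines this: "The Inclusion date will be considered as the reference start date".

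Only the third rule refers to inclusion. The section says the conventions serve both summary statistics and listings.

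SAP 14.1 sets the reporting window: "Adverse events that occurred after the inclusion visit and prior to study termination or Lost-to follow-up will be presented", for the Safety Population. It does not say whether an imputed start date decides membership of that window. SAP 17.7 compares start dates only with the cut-off date, which is an upper bound.

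Collection starts earlier than the SAP window. Protocol 10.2 states: "Serious cardiovascular and access site adverse events from inclusion (signing date of informed consent) to termination should be reported".

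Some outputs do not depend on the window. SAP 14.2 says "All AEs, ADEs, Device Deficiencies, SAEs and Deaths will be listed", with no date restriction. For unanticipated serious device effects, SAP 11.1 A says the absence of such effects "will be evaluated by analyzing all SAEs and device deficiencies (DD) collected at each visit".

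**The concern.** Setting an unknown day to the first of the month is a common convention, but for adverse events it is usually bounded below by the start of observation. Without that bound, an event known only to have occurred in the inclusion month is always placed on or before the inclusion date, whatever its true onset. Combined with a window that keeps only later events, the rule can remove from the tables the partially dated events that began soon after enrolment.

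Two related points follow from the same wording:

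- A totally missing date is set to the inclusion date, which is not strictly later than the inclusion visit.
- An event on the day of inclusion with a complete date is collected under Protocol 10.2 but falls outside SAP 14.1 read literally.

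What is at stake is the completeness of the safety summaries. The error runs one way: counts can be too low, never too high, which is the anti-conservative direction for safety.

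**Working it through.** The documents give no figure on this point, so there is none to reproduce. The check has three parts.

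**1. Worked example, using the SAP 5.2 study-day formula.** Study day = event date - inclusion date + 1 if the event is on or after inclusion, and event date - inclusion date if it is before. Take inclusion on 20 March 2017 and true onset on 28 March 2017 (illustrative dates).

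| What is known | Date used | Study day |
|---|---|---|
| Full date | 28 Mar 2017 | 28 - 20 + 1 = 9 |
| Month and year | 1 Mar 2017 | 1 - 20 = -19 |
| Year only | 1 Jan 2017 | -78 |
| Nothing | 20 Mar 2017 | 1 |

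The two partial dates fall before inclusion. The totally missing date falls on Day 1 and fails a strict *after*.

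**2. When this happens.** With the day missing, the imputed date is on or before inclusion exactly when the onset falls in the same calendar month as inclusion. If the onset is in a later month, the first of that month is already after inclusion. With day and month missing, the condition is the same calendar year. The shares below are therefore the chance that onset shares the month, or the year, of inclusion.

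**3. How often, given a partial date.** Inputs:

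- Inclusion period: 92 days, inclusion spread evenly. Protocol 4.3 says "As the study plans an inclusion period of approximately 3 months".
- Follow-up: up to day 107, from 15 days to M0 plus 92 days to M1 (SAP 5.3).
- Onset: uniform over the days considered (assumption).
- Calendar: first inclusion period starting 29 September 2016 (CIP date, SAP section 1). The last starts 28 June 2017, so that follow-up ends by 12 January 2018 (date in the extract file name, SAP 17.8). This gives 273 possible starting dates.

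Ranges over the 273 periods, day missing:

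| Onset | Imputed date on or before inclusion | Strictly before |
|---|---|---|
| Days 1-15 | 70.9-73.9% | 67.5-70.7% |
| Days 16-107 | 3.6-4.1% | 3.1-3.6% |
| Days 1-107 | 13.0-13.9% | 12.1-13.0% |

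Rough check on the last row, weighting the first two by their 15 and 92 days: (15 × 0.709 + 92 × 0.036)/107 = 0.130 and (15 × 0.739 + 92 × 0.041)/107 = 0.139.

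Day and month missing, onset in days 1-107: 42.5% to 100% on or before inclusion. The result depends on when enrolment ran: 43.4% for a start on 6 October 2016, 52.3% for 1 November 2016, and 100% for 1 January 2017, when all follow-up falls within one year.

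These are shares of events with a partial date, not of all events.

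**4. With a floor at inclusion.** Taking the later of the imputed date and the inclusion date moves both partial dates in the example from Day -19 and Day -78 to Day 1. Day 1 still fails a strict *after*, so the wording of 14.1 must change as well.

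**The case against.** The strongest objection is that the exclusion rests on a step the SAP does not state. No passage says the imputed date selects events for SAP 14.1, and that section can be read as restating the collection period rather than as a programmed filter. It also says that serious cardiovascular events and all deaths throughout the study will be reported. The derivation rules sit in the Appendix 2 specification, which is not among the documents reviewed and may already contain a floor. This stands, and it is why the point is put conditionally. But the SAP has an imputation rule for start dates and a window defined by onset, and no other rule linking them.

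Second, partial dates should be rare. Events during testing would normally carry the visit date. Serious cardiovascular and access-site events are due within 3 calendar days and deaths within 1 business day, and queries precede database lock. This also stands. However, the SAP's remark that missing dates should have been clarified follows the totally missing case and itself allows for unresolved ones.

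Third, the percentages depend on assumed inputs. M1 may come as early as 30 days after M0, and enrolment may not have lasted 92 days. Some of the periods start before the eCRF version date of 6 October 2016. Enrolment over 180 days from that date would raise the year-only share from 43% to 71%. The year-only range is therefore little more than a statement that the share could be large. The missing-day figures vary little across the calendar periods but still rest on uniform onset and the 107-day span.

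Fourth, the consequences are small. This is agreed.

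**Conclusion.** The concern holds and is minor. As written, SAP 17.6 can date an on-study event before inclusion, and nothing in SAP 14.1 or 17.7 prevents that event from being left out of the summary tables. Loss from the tables depends on imputed dates being used to apply the 14.1 window, which the SAP neither states nor rules out. The inclusion-day mismatch with Protocol 10.2 exists even when every date is complete.

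Under the stated assumptions, about 13-14% of events with a missing day over days 1-107 would be affected, nearly three quarters of those in the first 15 days. The absolute number cannot be estimated, because the documents give no count of partial dates, and it may be zero.

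The damage is limited. Events remain in the listings, and with fewer than 10 events SAP 14.1 produces only listings. The assessment of unanticipated serious device effects in SAP 11.1 A applies no start-date filter. The safety analysis is descriptive and the primary endpoint is not involved.

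**What to change.** - **SAP 17.6:** when the known part of the date is compatible with onset on or after inclusion, impute the later of (a) the first day of the known month or year and (b) the inclusion date. For an event recorded as occurring during testing, use the date of that visit.
- **SAP 14.1:** define the window as *on or after the inclusion date*. Floored dates and totally missing dates then count as on-study, and the window matches collection from consent in Protocol 10.2.
- **Appendix 2:** if the derivation specification already applies such a floor, state it in the SAP text.

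The cost is one sentence in 17.6 and a few words in 14.1. A condition that began before inclusion in the same month or year may occasionally be counted as on-study, which errs in the conservative direction.

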17.7. DATA INCLUDED IN THE ANALYSES AND CUT-OFF DATE

The final analyses will be performed using all data collected in the database up to the data cut-off date. Of all the termination dates of the subjects included in the study, the last termination visit date will be defined as the cut-off date and will be specified in the outputs.

Any data collected beyond the cut-off date will not be included in the analysis. Only data with an assessment date or event start date (e.g. vital sign assessment date or start date of an adverse event) prior to or on the cut-off date will be included in the analysis. For example, if the cut-off date is 15 June 2017 then an AE starting on 13 June 2017 will be reported, whereas an AE with start date on 17 June 2017 will not be reported.

All events with an event start date either before or on the cut-off date and an event end date after the cut-off date will be reported as "continuing at the cut-off date". The same rule will be applied to events starting either before or on the cut-off date and not having a documented end date. This approach applies, in particular, to adverse event and concomitant medication reports. For these events, the end date will not be imputed and therefore will appear as missing in listings.

If it is required to impute an end date to be able to perform a specific analysis (e.g. end date after the cut-off date) the cut-off date needs to be imputed as an end date. The imputed date will be displayed and flagged in the listings.

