5.5. LAST CONTACT DATE

The last contact date is defined as the latest complete date from the list below or the cut-off date, whichever comes first.

- Actual assessment dates (e.g. device electrical performances, Manual LV pacing threshold, ECG record, « In-Clinical LVAT » tests, etc.).
- Adverse events dates
- Device deficiency dates
- Protocol deviation dates
- Date of last recorded on date on “Medications”
- Date of device implant/re-intervention
- Date of Termination

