14.2. ANALYSIS OF ADVERSE EVENTS

The following AE summaries will be produced for all subjects in Safety set:

Overall Summary of AEs, ADEs, Device Deficiencies, SAEs and Deaths will be provided for number of subjects with at least one event and number of events

- Any AEs
 - Expected
 - Unexpected
 - Was Device Interrogation performed (Yes/No)
 - Related to procedure (Yes/No)
 - Related to device (Yes/No)
 - Outcome (Resolved/Death/Pending)
- Any ADEs
 - Expected
 - Unexpected
 - Was Device Interrogation performed (Yes/No)
- Any Device Deficiencies
 - Expected
 - Unexpected

LEVEA – Statistical Analysis Plan

- Issue resulted in any (serious) adverse event(Yes/No)
- Was reprogramming done (Yes/No)
- Device re-intervention (Yes/No)
- Device returned to Sorin (Yes/No)
- Subject discontinued from the study following the DD(Yes/No)
- Serious adverse events (SAEs)
- SAE (Other than Death)
- SAE Leading to Death
- Deaths
- Device related
 - ✓ Unexpected Serious Adverse Device Effect (SADE)
 - ✓ Expected SADE
- Procedure related
- Not device or procedure relationship
- Device related ISO (procedure and/or device related)
 - Unexpected Serious Adverse Device Effect (SADE)
 - Expected SADE

For the following -

- AEs
- ADEs
- Device deficiencies
- SAEs

events leading to Hospitalization will be analysed with the following details:

- Hospitalization required (Yes/No)
- Duration of Hospitalization (Summary statistics – Mean, SD, Q1, Median, Q3, Min, Max)
- Did it cause Permanent Disability/incapacity (Yes/no)
- Intervention to Prevent Life Threatening Injury or Permanent Damage (yes/No)
- Life Threatening Illness or Injury (Yes/No)

For the following -

- AEs
- ADEs

LEVEA – Statistical Analysis Plan

- Device deficiencies
- SAEs

events requiring treatment or medication will be analysed to provide the following:

- Treatment provided (Yes/No)
- Device programming required (Yes/No)
- Device re-intervention required (Yes/No)
- Any other intervention required (Yes/No)
- Led to change in cardiovascular medication since last visit (Yes/No)

For the following -

- AEs
- ADEs
- Device deficiencies
- SAEs

Outcome will be reported. Outcome can be any of the following:

- Final outcome pending
- Final outcome
- Resolved
- Death
- On-going or chronic
- Unknown

The following information for Device deficiencies will be summarized:

- Component involved (obtained from Device deficiency page of eCRF)
- Device Deficiency category (obtained from Device deficiency page of eCRF)

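### Where an end date must be imputed, SAP 17.7 uses the study-wide cut-off instead of the subject's last contact date, so a hospital stay could be credited with time nobody observed

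*SAP*

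**What the plan says.** SAP 17.7 sets a single cut-off for the study: "the last termination visit date will be defined as the cut-off date". Events that start by then and end later are reported as continuing at the cut-off. Events with no end date are treated alike: "The same rule will be applied to events starting either before or on the cut-off date and not having a documented end date". The default is not to impute: "For these events, the end date will not be imputed and therefore will appear as missing in listings".

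An exception follows. If a specific analysis cannot be done without an end date, "the cut-off date needs to be imputed as an end date". The SAP's own example of this is an event whose end date falls after the cut-off. On disclosure it adds: "The imputed date will be displayed and flagged in the listings".

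Three other places bear on this:

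- SAP 14.2 plans "Duration of Hospitalization (Summary statistics" with mean, SD, quartiles, median, minimum and maximum, for AEs, ADEs, device deficiencies and SAEs that lead to hospitalization. It does not say which dates define a stay.
- SAP 5.5 already holds a subject-level date: "The last contact date is defined as the latest complete date from the list below or the cut-off date, whichever comes first". The list includes adverse event dates and the termination date. Section 17.7 does not refer to it.
- SAP 14.1 reports adverse events by listing only if there are fewer than 10.

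**The concern.** A subject completes the study at M1 (Protocol 6.2), and serious cardiovascular and access site events are collected from consent to that subject's termination (Protocol 10.2). SAP 14.1 likewise limits event onset to the time before the subject's termination or loss to follow-up. Onset is thus bounded at subject level, while SAP 17.7 places the end of an open event at study level. For anyone who terminated before the last subject, the two horizons differ.

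This has two consequences. First, the label says that an event was continuing on a date when the subject was no longer followed. No exception is written for death, withdrawal or loss to follow-up. Second, if the imputation is used for length of stay, the reported duration includes unobserved time, and how much depends on when the subject happened to be included. The mean, SD and maximum are sensitive to a single such record.

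**Working it through.** **Inputs**

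- Inclusion period about 3 months, follow-up 3 months, study about 6 months (Protocol synopsis and 4.3).
- Participation at most 3 months per subject (Protocol 4.3).
- M0 at 0–15 days after inclusion; M1 at 30–92 days after M0 (SAP 5.3, Table 1).
- One month = 30.4375 days (SAP 17.5).
- 59 subjects (Protocol 4.2).

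**The plan's own figure.** 3 + 3 = 6 months, as stated.

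**Gap between own termination and cut-off**

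Gap = (latest termination of any subject) − (own termination). The inclusion period is 3 × 30.4375 = 91.3, taken as 91 days. The first subject enters on day 0, the last on day 91, and a subject who completes M1 terminates on that day.

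1. Equal follow-up F for all: (91 + F) − F = **91 days**.
2. First subject has M0 at once and M1 at 30 days, so ends on day 30. Last subject is held to 3 months: 91 + 91 = day 182. Gap = 182 − 30 = **152 days**.
3. Window extremes: the last subject ends on day 91 + 15 + 92 = 198. Gap = 198 − 30 = **168 days**, or 5.5 months.

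Case 3 uses 15 + 92 = 107 days (3.5 months) for the last subject, which the SAP windows allow but which exceeds the protocol's 3-month maximum. Day 198 (6.5 months) also exceeds the approximate 6-month study duration. Case 2 removes both excesses. A subject who stops on the day of inclusion lies outside these cases; with the cut-off of case 3 the gap would be 198 days.

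The average gap is smaller. Assuming uniform inclusion and equal follow-up, the expected gap is 91.3 × 59/60 − 91.3/2 = 89.8 − 45.7 = about 44 days. A simulation with M0 and M1 uniform over their windows gives about 66 days.

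**Effect on a summary (assumed data).** Take ten stays of 7 observed days each, one of them open at own termination. The mean is (10 × 7 + gap)/10.

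| Gap (days) | Mean | Maximum | Median |
|---|---|---|---|
| 0 | 7.0 | 7 | 7 |
| 91 | 16.1 | 98 | 7 |
| 152 | 22.2 | 159 | 7 |
| 168 | 23.8 | 175 | 7 |

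**With the SAP 5.5 date.** If nothing dated later than termination is on record, last contact is the termination date. The gap is then 0 and the open stay counts as 7 days, a minimum.

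**The case against.** A reader might infer that every open-ended event receives the cut-off as its end date, so that event durations in general are inflated. The documents do not support that. Non-imputation is the default, the exception is conditional, and an imputed date is flagged in the listings. No summary of adverse event duration is planned. Length of stay is the only candidate, and it may rest on a recorded discharge date instead of the event end date. The dataset specification that SAP 17.8 and Appendix 2 refer to is not among the documents, so this cannot be settled here.

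The route to harm is also narrow. It needs a stay open at termination, no end date obtained by database lock, at least 10 adverse events, and a decision to impute. For a subject who completes the study, it means being in hospital at the M1 testing visit. Sites are queried on omissions (Protocol 9.1), and updates on unanticipated device effects are due until the end of the study (Protocol 10.2), so it is too strong to say that nothing can be learned after a subject's termination. Where a documented end date lies beyond the cut-off, the rule shortens the duration.

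All of this stands and limits the point. Three things remain. Flagging is promised for listings, not for the tables that show the mean and maximum. The threshold of 10 counts adverse events, not stays, so ten events with only a few stays would still be tabulated. And the continuing-at-cut-off label applies by default, with or without imputation. Later information does not argue for the cut-off either: a documented end date removes the need to impute, and a later dated adverse event entry would move the SAP 5.5 date.

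**Conclusion.** The point holds in a limited form. SAP 17.7 labels open events as continuing on a date beyond the observation of every subject who terminated earlier, and it prescribes that same date whenever an end date must be imputed. Only the length-of-stay summary in SAP 14.2 could be affected, provided that it uses an imputed end date and that at least 10 adverse events are reported. For a subject who completes M1, the excess is then at most about 91, 152 or 168 days, depending on which follow-up limits are applied.

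These figures assume a 3-month inclusion period and visits within the windows; longer recruitment would raise them. Whether any such stay will occur cannot be known from the documents. The matter is confined to descriptive safety reporting. The primary endpoint, its test and the sample size are untouched.

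**What to change.** In SAP 17.7, for events with no documented end date:

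- where an analysis needs an end date, impute the subject's last contact date (SAP 5.5), which is already capped at the cut-off;
- label these events as ongoing at last contact;
- footnote the resulting durations in the summary tables, not only in the listings, as minimum values.

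The handling of documented end dates after the cut-off can stay as it is. In SAP 14.2, add which dates define a hospital stay, so that it is clear whether the imputation applies at all.

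The cost is a few sentences and the use of a date the SAP already defines. The downside is that imputed durations become lower bounds and may understate the true stay, which the footnote tells the reader.
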